11.5. Vital Sign Measurements

Vital signs (including sitting blood pressure, heart rate, respiration, and temperature) will be measured at screening, on Day 1 of each cycle, at the Treatment Discontinuation Visit, and at the 28-Day Post Treatment Safety Follow-up visit. At unscheduled visits, vital signs will be measured. Height, weight and BSA will be measured at screening, on Day 1 of each cycle, at the Treatment Discontinuation Visit, and at the 28-Day Post Treatment Safety Follow-up visit.

Baseline is defined as the latest value collected on or before the date when the first dose of study treatment is administered. If multiple values are present for the same date, the mean of these values will be used as the baseline.

Summary statistics (n, mean, median, StdDev, Q1, Q3, Min, and Max) of observed and change from baseline values will be presented.

Change from baseline in vital sign values by visit will be displayed in cross-tabulations. For each vital sign parameter, the change from baseline to lowest reported value and highest reported value will be presented. In [Table 2](#): Normal Range of Vital Sign Measurements normal ranges are reported.

Temperature in Fahrenheit will be converted to Celsius with the following formula:

- Temperature in Celsius = (temperature in Fahrenheit – 32) * 5/9.

Table 2: Normal Range of Vital Sign Measurements

Test	Age Group (years) ^a	Normal Range (Unit)
Diastolic Blood Pressure	< 2	[34,66] (mmHg)
	2 to 5	[34,74] (mmHg)
	6 to 8	[35,80] (mmHg)
	9 to 13	[37,87] (mmHg)
	14 to 16	[40,91] (mmHg)
	≥ 17	[40,89] (mmHg)
Systolic Blood Pressure	< 2	[58,112] (mmHg)
	2 to 5	[60,125] (mmHg)
	6 to 8	[65,131] (mmHg)
	9 to 13	[68,141] (mmHg)
	14 to 16	[76,153] (mmHg)
	≥ 17	[70,139] (mmHg)
Pulse Rate	1 to 2	[95, 178] (bpm)
	3 to 7	[62, 124] (bpm)
	8 to 15	[48, 110] (bpm)
	≥ 16	[60, 100] (bpm)
Temperature	All	[35, 38] (°C)
Respiratory Rate	1 to 3	[24,50] (BPM)
	4 to 6	[22,34] (BPM)
	7 to 12	[18,30] (BPM)
	13 to 21	[12,16] (BPM)

^a Years reached at the time of the assessment.

Listings will be provided for all vital sign parameters for the ITT population.

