6.4.2.1. Physical Examinations (Including Vital Signs)

A complete physical examination will include (as applicable) the examination of general appearance, skin, neck, eyes, ears, nose, throat, lungs, heart, abdomen, back, lymph nodes, extremities, vascular and neurological (Section 6.4.2.8). For other indicated areas, based on medical history and/or symptoms, examinations will be performed.

Physical examination will be source documented only; however significant findings that were present prior to the signing of the ICF/IAF must be included in the Medical History page on the subject's eCRF. Clinically significant new findings that begin or worsen after informed consent/assent must be recorded on the AE page of the subject's eCRF.

At screening, the Investigator or designee performing the physical examination will characterize the findings as either normal or abnormal in the source. If abnormal, a description of the abnormality and clinical importance should be source documented. Clinically significant changes from screening/baseline will be recorded in the AE section of the eCRF.

Vital signs assessment will include temperature, blood pressure, heart rate and respiratory rate. On-treatment vital sign measurements will be source documented only; however, if an abnormal (out of range) value is reported at any given visit and clinically significant, that parameter should be collected in the eCRF at every subsequent scheduled visit until it returns to normal or not clinically significant (NCS), and recorded as an AE if appropriate.

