11. SAFETY ANALYSIS

The purpose of this section is to define the safety parameters for the study. All summaries of safety data will be conducted using the Safety Population and will be presented by tumor type/disease indication, and in aggregate. Safety measurements will include AEs, clinical laboratory information, vital sign measurements, SPM, pregnancy status, and deaths. Individual subject listings will be provided to support the tables.

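### SAP 11.5 plans full on-treatment summaries of four vital signs that the protocol enters in the eCRF only after a clinically significant abnormality

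*SAP*

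**What the plan says.** SAP 11.5 (Vital Sign Measurements) has vital signs measured at screening, Day 1 of each cycle, treatment discontinuation and the 28-day safety visit. Height, weight and BSA are in the same section. Three kinds of table are planned:

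- Descriptive summaries: "Summary statistics (n, mean, median, StdDev, Q1, Q3, Min, and Max) of observed and change from baseline values will be presented".
- Cross-tabulations, laid out visit by visit, of how values moved from baseline.
- Extremes, parameter by parameter: "the change from baseline to lowest reported value and highest reported value will be presented".

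A listing of all vital sign parameters is also planned for the ITT Population. The opening of SAP 11 fixes the population for the tables: "All summaries of safety data will be conducted using the Safety Population".

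Protocol 6.4.2.1 names the parameters: "Vital signs assessment will include temperature, blood pressure, heart rate and respiratory rate". It then restricts what is collected: "On-treatment vital sign measurements will be source documented only". The exception applies "if an abnormal (out of range) value is reported at any given visit and clinically significant". In that case the parameter concerned is entered in the eCRF at later scheduled visits until it is normal or judged not clinically significant, and is recorded as an AE where appropriate. Protocol 14.2 (Data Management) says the clinical database is filled from the eCRF.

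**The concern.** The SAP tables presuppose that every treated subject has a value in the database at each scheduled visit. Under the protocol, whether an on-treatment value is there depends on what earlier values of the same parameter were, so the sample is selected on the outcome being summarised.

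Baseline may exist for everyone while later visits hold only flagged subjects. A table laid out by visit would then look like a trend in the treated population when it is not one. Lowest and highest on-treatment values would be missing for most subjects, because their measurements never leave the source documents. The SAP does not mention the conditional collection, name another data source or limit these tables to flagged subjects.

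**Working it through.** The plan gives no figure to reproduce, so the check has two parts.

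**1. Which results are affected.**

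- *Parameters.* The protocol rule covers temperature, blood pressure, heart rate and respiratory rate. Height, weight and BSA have their own sections (6.4.2.2 to 6.4.2.4), are taken on Day 1 of each cycle and are outside the rule.
- *Timing.* The rule is confined to on-treatment values. Screening values fall outside it. The protocol does not say whether End of Treatment and 28-day follow-up values count as on-treatment.
- *Which values are entered.* The text clearly requires entry at visits after the trigger. It does not clearly say that the triggering value itself is entered. Entered values can include the return to normal, so they come from subjects with a prior abnormality but need not all be abnormal.
- *Which tables.* All three kinds of table, and the listing, draw on the same incomplete data. In the SAP, the words by visit attach to the change cross-tabulations, not to the sentence on summary statistics.

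**2. Illustrative size.** The documents give no abnormality rate, so the inputs below are assumptions, except the range.

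- Range: systolic 70 to 139 mmHg, from SAP Table 2 for age 17 and over. That this is the range sites use for out of range is itself an assumption, and about 80% of subjects are to be under 17 (Protocol 4.1).
- Model: value = subject mean + visit noise, with no drug effect and no trend. Baseline follows the same model.
- Subject means: centre 112, 118 or 125 mmHg, between-subject SD 9. Visit noise SD: 6, 8 or 10.
- Six cycles. Half of out-of-range values are judged clinically significant.
- Entry starts after a trigger and stops once a value is normal or not clinically significant.
- Shift = mean of entered values minus mean of all values. Values per stratum visit = 20 × proportion entered.

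Ranges over the nine combinations:

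| Reading of the rule | Subjects ever contributing | Entered per visit | Per visit, stratum of 20 | Mean of entered values (mmHg) | Shift (mmHg) | Mean change (true value 0) |
|---|---|---|---|---|---|---|
| Only visits after the trigger | 1.3% to 26.9% | 0.3% to 7.5% | 0.06 to 1.5 | 125 to 138 | +9 to +21 | about 0 |
| Triggering visit also entered | 1.4% to 30.1% | 0.5% to 12.5% | 0.1 to 2.5 | 133 to 141 | +15 to +26 | +3.2 to +8.5 |

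One worked line: with centre 125, noise SD 10 and only later visits entered, the mean of entered values is 134.4 against 125.0 for all, so the shift is 134.4 − 125.0 = +9.4 mmHg. Entered values are 20 × 0.075 = 1.5 per visit.

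On the first reading, change is near zero because baseline and later values share the subject's own mean and the noise at the trigger is not carried forward. That result belongs to this model. With a drug effect, a trend or correlated noise, the change would differ and would still describe flagged subjects only. The shift is upward here because the upper limit is the nearer one. A parameter that tends to fail at its lower limit would shift downward.

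**The case against.** The strongest reply is that nobody reading these two documents has seen the eCRF. SAP 11.5 is written as though the data will exist: it has a Fahrenheit conversion, a rule for several values on one date, normal ranges by age at assessment and a listing of all parameters. The SAP also has no laboratory results section, in keeping with Protocol 6.4.2.6, which keeps laboratory values off the laboratory eCRF. That could suggest its authors knew the collection rules and still expected vital signs. This is only suggestive, since the opening of SAP 11 does list laboratory information among the safety measurements. What stands is that the eCRF may hold everything. In that case Protocol 6.4.2.1 is the text that is wrong, and the two documents still conflict.

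Two further replies are fair. The tables print n, so a small n would show against the column total. Clinically significant findings also go to the AE page where appropriate, so individual safety capture is not lost. Both limit the harm. Neither makes the tables valid.

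A reader might infer that all of SAP 11.5 should be deleted. The documents do not support that: height, weight, BSA and screening values are outside the protocol rule.

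A reader might also infer a tenfold overstatement. If 2 of 20 subjects rose by 25 mmHg and the rest did not change, the true mean change would be 2 × 25 / 20 = +2.5 mmHg, the database would show +25, and the shift table would show 100% abnormal. Those inputs are invented, and +25 needs the rise to appear in the entered values, either because the triggering value is entered or because the rise persists. The 100% needs a denominator of subjects with data. The SAP does not set one, and on the Safety Population the figure is 2/20 = 10%, which is correct.

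**Conclusion.** The conflict is real, and nothing in either document reconciles it. For the four parameters on treatment, the planned summaries would rest only on subjects with a prior clinically significant abnormality in that parameter. Observed means would be biased. The size and direction of the effect on change scores cannot be settled from the documents, because they depend on whether the triggering value is entered and on unstated abnormality rates.

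The conclusion that the sample is selected on the outcome needs only that the eCRF was built as Protocol 6.4.2.1 describes. The simulated sizes need every assumption listed with them and should be read as illustration. The consequence is confined to descriptive safety tables. No efficacy result or stage decision depends on them.

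**What to change.** First check the built eCRF.

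- **If it follows Protocol 6.4.2.1:** for temperature, blood pressure, heart rate and respiratory rate, replace the on-treatment summary, change and lowest/highest tables in SAP 11.5. In their place give the number and percentage of Safety Population subjects with at least one clinically significant on-treatment abnormality, by parameter, plus the listing. State in the SAP that on-treatment values were collected selectively. Say whether the triggering value is entered and how an abnormality is identified, because one at a subject's last scheduled visit would otherwise leave no later entry to count.
- **If it collects all scheduled values:** correct Protocol 6.4.2.1 and keep the tables.

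In either case keep the screening/baseline summaries and the height, weight and BSA summaries, and state whether End of Treatment and 28-day follow-up values count as on-treatment.

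The first route costs SAP wording and produces fewer tables, with no new data. Collecting every scheduled value instead would also resolve the conflict, at the price of extra data entry.

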6.2. Treatment Period

The subject will begin treatment upon re-confirmation of eligibility (ie, safety assessments) and subsequent enrollment. The subject must start treatment within 28 days of signing the ICF/IAF. For all subsequent visits, an administrative window of ± 3 days is permitted unless noted otherwise for a particular assessment. Brain and spine MRI assessments can be conducted within 7 days prior to the scheduled timepoint (ie, during study drug rest period). Study visit windows should take into account the subject's investigational product (IP) supply and administration.

Note: Safety laboratory (hematology, serum blood chemistry) and physical examinations do not need to be repeated on Cycle 1, Day 1 if performed within 7 days of starting treatment unless clinically indicated; however, for FCCBP/FCBP subjects, a urine or serum pregnancy test must be performed to assess subject eligibility 10 to 14 days prior to and again within 24 hours prior to the first administration of pomalidomide. The pregnancy test 10 to 14 days prior to initiation of pomalidomide however may be omitted, at the discretion of the investigator, for any FCCBP/FCBP who has high acuity disease requiring immediate treatment with pomalidomide. The pregnancy test within 24 hours prior to the first dose of pomalidomide is required to be performed (refer to Section 6.4.2.9).

The Treatment Period is defined as the time starting from first study drug administration (Cycle 1, Day 1) until permanent study treatment discontinuation. Subjects will be administered pomalidomide on Days 1 to 21 of each 28-day treatment cycle for a maximum of 24 cycles. Pomalidomide will not be administered on Days 22 through 28 of the 28-day treatment cycle.

The following evaluations will be performed at the frequency specified in the Table of Events (Table 4) and further detailed in the protocol referenced Section 6.4. The evaluations should be performed prior to dosing on the visit day, unless otherwise specified.

- Reconfirm eligibility (Cycle 1, Day 1 only)

- IRT registration (Day 1 of each treatment cycle)
- Enrollment via IRT: Day 1, Cycle 1 only
- Concomitant medications and procedures
- Adverse event evaluation
- Assessment of SPM
- Physical examination (including vital signs)
- Height
- Body weight
- BSA calculation
- Lansky/Karnofsky performance status. Karnofsky will be utilized for subjects age ≥ 16 years and Lansky will be utilized for subjects age < 16 years.
- Hematology

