6.4.2.4. Body Surface Area Calculation

Body surface area, in m², will be calculated using the following formula, where weight (W) is in kg and height (H) is in cm (Dubois, 1916):

$$BSA = (W^{0.425} \times H^{0.725}) \times 0.007184$$

The subject's pomalidomide dose should be calculated on the first day of Cycle 1 based upon the subject's current BSA. Measurements of the subject's height and body weight will be repeated on Day 1 of each subsequent cycle and BSA recalculated at these visits.

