4. INVESTIGATIONAL PLAN

4.1. Overall Study Design and Plan

This is a Phase 2 multicenter, open-label, study to assess efficacy, safety and PK of pomalidomide in children and young adults aged 1 to 20 years, inclusive, with one of four types of recurrent or progressive primary brain tumors. Pomalidomide will be administered as gelatin capsules and oral suspension to subjects once daily on days 1 to 21 of a 28-day cycle.

The study will consist of four tumor types, one for each of the following primary brain tumors: high-grade glioma, medulloblastoma, ependymoma, and DIPG. Enrollment and treatment of subjects in each of these four tumor types will run in parallel to one another.

The primary endpoint is the objective response and long-term stable disease rate (ORSDR), defined as the proportion of subjects achieving either an objective response (OR), either a partial response (PR) and/or a complete response (CR), or a long-term SD, defined as SD maintained for ≥ 6 cycles of pomalidomide (≥ 3 cycles for the DIPG tumor type/disease indication).

Each tumor type/disease indication incorporates the Simon's Optimal Two-stage study design.

During the study, a data monitoring committee (DMC) will convene on a regular basis to review safety data and to make recommendations about the study continuation or certain tumor type/disease indication as appropriate, based on the totality of the safety data and interim analysis decision-making data (if needed).

The study will be conducted in compliance with the International Council for Harmonisation (ICH) of Technical Requirements for Registration of Pharmaceuticals for Human Use/Good Clinical Practice (GCP) and applicable regulatory requirements.

The study will consist of 3 periods: Screening Period, Treatment Period, and Follow-up Period, outlined below (Figure 1):

Screening Period

The Screening Period will start from the time of signing the informed consent form (ICF)/informed assent form (IAF) and will last no more than 28 days, at which time the Treatment Period will begin (Cycle 1 Day 1). The subject's screening procedures are to occur during the Screening Period within 28 days prior to dosing on Cycle 1 Day 1.

Treatment Period

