11.2. Adverse Events of Special Interest

Selected TEAEs and serious AEs (SAEs) will form AEs of special interest (AESI), including second malignancies and cardiovascular events, as determined by the mechanism of action, known class effects, or TEAEs observed to date will be summarized. Standardized MedDRA queries (SMQs) will be used in the search strategy for some of the selected AEs of special interest related to study drug, intending to aid in case identification. The groupings of selected AEs, described by one phrase or topic term will be determined by clinicians based on SMQ or relevant search terms and provided to statistician, prior to database lock.

Analysis of AEs of special interest will be presented with tabulations for: summary of TEAEs of interest by category, TEAEs of interest, CTCAE grade 3 or 4 TEAEs of interest, TEAEs of interest related to study medication, CTCAE grade 3 or 4 TEAEs of interest related to study medication, serious TEAEs of interest, serious TEAEs of interest related to study medication, serious CTCAE grade 3 or 4 TEAEs of interest, TEAEs of interest leading to study medication discontinuation, TEAEs of interest by CTCAE maximum grade 1 or 2 and 3 or 4 and TEAEs of interest by CTCAE maximum grade. The following AE of interest categories and preferred terms include, but are not limited to:

- neutropenia;
- febrile neutropenia;
- infection;
- thrombocytopenia;
- hemorrhage and bleeding;
- neuropathy;
- DVT (deep vein thrombosis);
- PE (pulmonary embolism);
- SPM (second primary malignancies);
- muscular weakness;
- glucose intolerance;
- mood alteration;
- cataract;
- cardiovascular events/dysrhythmia;
- fluid retention/edema;
- hematopoietic cytopenias.

The following summaries will be provided for above-mentioned TEAEs of special interest:

- All TEAEs;
- TEAEs with severity of grade 3 and/or 4;

- TEAEs related to pomalidomide;
- Serious TEAEs;
- Serious TEAEs with severity of grade 3 and/or 4;
- Serious TEAEs related to pomalidomide.

All AESIs will be identified by appropriate MedDRA PT.

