Calculations using dates (eg, subject's age or relative day after the first dose of study drug) will adhere to the following conventions:

- Study days after the start day of study drug will be calculated as the difference between the date of interest and the first date of dosing of study drug (eg, pomalidomide) plus 1 day. The generalized calculation algorithm for relative day is the following:
 - If TARGET DATE \geq DSTART then STUDY DAY = (TARGET DATE – DSTART) + 1;
 - Else use STUDY DAY = TARGET DATE – DSTART.

Note that Study Day 1 is the first day of treatment of study drug. Negative study days are reflective of observations obtained during the baseline/screening period. Note: Partial dates for the first study drug are not imputed in general. All effort should be made to avoid incomplete study drug start dates. Some analyses may exclude subjects without study drug start date. The SAP may be amended on a case-by-case basis, including guideline and suggestion such as imputing Day 1 by consent date of treated subject.

- Age (expressed in days) is calculated: AGE = CONSENT – DATE of BIRTH + 1. In practice, age will be transformed to years by dividing the difference by 365.25 days, then truncating.
 - Preference is for using calculated age from clinical database. When not available, calculated age from eCRF or IVRS may be used.
 - Partial birth date: impute missing day as 15th of the month; impute missing month as July; set missing age for missing year. Should the imputed age succeed an earlier assessment date collected for that subject, the imputed month will be set to the month preceding the assessment date.
- Intervals that are presented in weeks will be transformed from days to weeks by using (without truncation) the following conversion formula:

$$\text{WEEKS} = \text{DAYS} / 7.$$

- Intervals that are presented in months will be transformed from days to months by using (without truncation) the following conversion formula:

$$\text{MONTHS} = \text{DAYS} / 30.4375.$$

3. Calculations of Cycles

Treatment will commence on Day 1 and planned cycle lengths are 28 days. Day 1 of treatment is defined as the first day of actual study drug administration. Day 1 of a cycle is defined as day 1 of study drug for the given cycle as recorded on the eCRF.

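### Height and weight are summarised only as raw values and raw change in patients aged 1 to 20, so failure to gain weight or slowed height in children who stay on treatment for many cycles can go unseen

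*SAP*

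**What the plan says.** The study enrols "children and young adults aged 1 to 20 years, inclusive" (SAP 4.1). SAP 11.5 states: "Height, weight and BSA will be measured at screening, on Day 1 of each cycle, at the Treatment Discontinuation Visit", and again at the 28-day safety visit. Protocol 6.4.2.4 agrees for the treatment period: "height and body weight will be repeated on Day 1 of each subsequent cycle and BSA recalculated at these visits". Treatment runs on "Days 1 to 21 of each 28-day treatment cycle for a maximum of 24 cycles" (Protocol 6.2).

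The planned output in SAP 11.5 is: "Summary statistics (n, mean, median, StdDev, Q1, Q3, Min, and Max) of observed and change from baseline values will be presented". The section adds cross-tabulations by visit and, for each vital sign parameter, the change to the lowest and highest value. Table 2 of the SAP gives age-banded normal ranges for blood pressure, pulse and respiratory rate, and one range for temperature. It has no row for height, weight or BSA.

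SAP 11 presents safety summaries by tumor type and in aggregate. SAP 11.1.2 adds age bands, but only for selected TEAE tables. SAP 4.3 confirms that there is no comparator. Neither document plans a z-score, percentile, growth velocity or expected-growth comparison.

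**The concern.** Expected change in height and weight is positive in a growing child, depends strongly on age, and is about zero in a fully grown subject. A pooled raw change mixes these. A child who gains no weight, or grows at half the normal rate, shows a raw change of zero or more and so looks the same as a stable young adult. The by-visit mean also moves as the age mix of those still on treatment changes. Without a control arm or an age split, nothing else in these tables separates normal growth from departure from it.

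At stake is whether the height and weight tables can be interpreted for the children treated longest. The SAP already accepts the principle for other measures: Table 2 is age-banded for three kinds of vital sign, using age at the time of assessment. Height and weight, which depend at least as much on age, are left raw.

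**Working it through.** **Inputs from the documents.** Ages 1 to 20; up to 24 cycles; "planned cycle lengths are 28 days" (SAP Appendix A2); 30.4375 days per month and 365.25 days per year (SAP Appendix A2).

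**Assumed inputs, not in the documents.** Normal weight gain of 2 to 3 kg/year in a 15 kg child; normal height growth of 6 cm/year at school age (range 4 to 8) and about 0 when fully grown.

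**1. Maximum time on treatment.** 24 × 28 = 672 days; 672 / 30.4375 = 22.1 months; 672 / 365.25 = 1.84 years. The documents give no growth figure to reproduce.

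**2. Weight, 15 kg child with no gain (raw change = 0).** Expected gain = rate × days / 365.25. Shortfall = expected gain / (15 + expected gain).

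| Day | Years | Expected gain (kg) | Expected weight (kg) | Shortfall |
|---|---|---|---|---|
| 56 (Cycle 3 Day 1) | 0.153 | 0.31 to 0.46 | 15.31 to 15.46 | 2 to 3% |
| 168 (Cycle 7 Day 1) | 0.46 | 0.92 to 1.38 | 15.92 to 16.38 | 6 to 8% |
| 672 (maximum) | 1.84 | 3.68 to 5.52 | 18.68 to 20.52 | 20 to 27% |

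**3. Height, growth at half the normal rate.** At 6 cm/year: 6 × 0.46 = 2.8 cm expected at 168 days against 1.4 cm observed; 6 × 1.84 = 11.0 cm expected at 672 days against 5.5 cm observed. Over 4 to 8 cm/year, the 672-day figures are 7.4 to 14.7 cm expected and 3.7 to 7.4 cm observed. All the observed changes are positive, while a fully grown subject shows 0.

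**4. Mean over a mixed-age stratum (simulation, all growth inputs assumed).** Twenty subjects, ages uniform from 1 to under 21. Baseline weight in kg: 8 + 2.4 × age under 10, 32 + 5 × (age − 10) from 10 to under 16, and 60 from 16. Gain in kg/year: 2 to 3, 3.5 to 5, and 0 to 1 in those bands. Raw change = (baseline + expected gain) × (1 − shortfall) − baseline. Mean raw change in kg:

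| Day | Normal growth | All 5% below expected | All 10% below expected |
|---|---|---|---|
| 56 | +0.4 | −1.6 | −3.5 |
| 168 | +1.2 | −0.8 | −2.8 |
| 336 | +2.3 | +0.3 | −1.8 |
| 672 | +4.6 | +2.5 | +0.3 |

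At 672 days a uniform 10% shortfall gives no mean loss, and only about 25% of subjects, the fully grown ones, have a negative raw change. At 56 days both shortfalls are plainly visible. At 672 days the SD of individual raw change from growth alone is about 2.6 kg, so a fluid gain of 1 to 2 kg would not stand out.

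**The case against.** The case against is strong on several points.

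- **Duration.** 672 days is the ceiling. Treatment stops at progression, and the design rates of 10% and 40% for response or long-term stable disease imply that 60 to 90% of evaluable subjects would have neither. Many would therefore be off treatment by about Cycle 7 (Cycle 4 for DIPG). This stands and limits the point to long-stay subjects.
- **Fluid retention.** Growth and fluid both raise weight, so growth confounds fluid gain; it does not offset it. "fluid retention/edema" is also tabulated directly as an AE of special interest (SAP 11.2). This stands.
- **Risk profile.** A reader might infer that pomalidomide's main toxicities act on weight or growth. Protocol 1.2.4 names myelosuppression as the main toxicity, and 1.2.3 names fatigue, anemia and neutropenia as most frequent. Peripheral edema leads only in adult myelofibrosis. Impaired growth appears only as a consequence of radiation (1.1.2).
- **Scope of the sentence.** It does not name height or weight, and Protocol 6.4.2.1 does not count them as vital signs. Including them is an inference from placement. If it is wrong, SAP 11.5 plans no post-baseline summary of them at all.
- **Other routes.** Clinically significant changes become AEs, individual listings are planned, and the change-to-lowest table would show abrupt loss if height and weight count as vital sign parameters. This stands for abrupt loss. It does not cover failure to gain or slowed height, where the value never falls below baseline.
- **Attribution.** Z-scores would not isolate a drug effect either. There is no control arm, many subjects may have had radiation, and corticosteroids are permitted (Protocol 8.1.2). This stands and governs how the result should be worded.

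**Conclusion.** The point holds as a minor reporting gap. Raw change in height and weight cannot show departure from expected growth in children treated for many cycles. For a 15 kg child with no gain, the unseen shortfall is about 6-8% at 168 days and 20-27% at 672 days, under the assumed 2 to 3 kg/year; it is 2-3% at 56 days. The percentages rest on those assumed rates. That a growing child's shortfall can sit behind a zero or positive raw change requires only that the expected change is positive.

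A reader might infer that 22 months of normal growth would hide drug-related weight loss and fluid retention across the trial. The documents do not support that. Early or abrupt loss remains visible, edema has its own tabulation, and 22 months is a maximum that few may reach. No endpoint, sample size, decision rule or safety trigger is affected.

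**What to change.** In SAP 11.5, state explicitly that height and weight are summarised. Keep the raw tables and add:

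- change from baseline in age- and sex-standardised height and weight z-scores, using age at each measurement, for subjects within the age range of one named public growth reference (for example the CDC reference; CDC is already in the SAP abbreviation list);
- a count of subjects whose z-score changes by a threshold fixed before database lock, for example 0.5 SD or more, with falls and rises shown separately;
- a flag for subjects with imputed birth dates. Protocol 6.1.2 collects date of birth only where local rules allow, and SAP Appendix A2 section 4.6 imputes a missing month as July, so age can be wrong by about half a year;
- a statement that the tables describe departure from expected growth and do not attribute it to pomalidomide, given prior radiation and corticosteroid use.

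The cost is a small amount of programming and no new measurements, provided that on-treatment height and weight are in the eCRF. That should be confirmed, because Protocol 6.4.2.1 keeps on-treatment vital signs mainly in source documents. Z-scores will mean less near age 20.
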